7.2.5 Long-term Follow-up

Following the SFU visit, there will be an LTFU period **during which data will be collected on the subjects' health condition, disease status, and subsequent anticancer treatment.**

Also, for subjects who discontinued study treatment without confirmed disease progression or start of subsequent anticancer treatment, tumor assessments will continue during LTFU every 12 weeks (\pm 2 weeks) for up to 3 years after last subject enrolled or until confirmed disease progression, start of subsequent anticancer treatment, death, withdrawal of consent, loss to follow-up, or end of study.

Subjects who had confirmed disease progression or started subsequent anticancer treatment, will be followed via telephone every 12 weeks (\pm 2 weeks) for assessment of survival and documentation of anticancer treatment. Subjects will be followed for up to 3 years after last subject enrolled or until withdrawal of consent, **loss to follow-up, or subject death, whichever occurs first.**

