7.5 Radiological Imaging Assessment

The extent of disease will be evaluated by contrast-enhanced MRI/CT according to **RECIST 1.1** ([Appendix D](#)). All radiological imaging will be performed as indicated in the Site Imaging Manual provided by the central imaging core laboratory. In order to reduce radiation exposure for subjects, low dose CT should be utilized whenever possible.

The screening scans must be performed within 28 days prior to enrollment and will be used as baseline. All subsequent scans will be performed in the same manner as at screening, with the same contrast, preferably on the same scanner. Radiological assessment must include MRI/CT of the chest, abdomen and pelvis, as well as assessment of all other known sites of disease as detailed within the Site Imaging Manual. Magnetic resonance imaging (MRI) of the brain should be performed if signs or symptoms suggestive of central nervous system metastases are present.

The same imaging modality, MRI field strength and intravenous and oral contrast agents should be used at screening should be used for all subsequent assessments. Liver specific MRI contrast agents should not be used. To reduce potential safety concerns,

macrocyclic gadolinium contrast agents are recommended per National Health Institute guidelines, or follow local standards if more rigorous.

During treatment and follow-up radiological imaging of the chest, abdomen, pelvis, as well as all other known sites of disease, will be performed independent of treatment cycle every 6 ± 1 weeks for the first 4 response assessments. After **four** 6-week response assessments, radiological imaging and tumor assessment will be performed every 12 ± 1 weeks. Radiologic imaging and tumor assessment will be performed until disease progression, start of new anticancer treatment, death, withdrawal of consent or until end of study. Imaging may also be performed more frequently if clinically necessitated at the discretion of the managing physician. Radiographic response (complete response, partial response) requires confirmation by a repeat, consecutive scan at least 4 weeks after the first documentation of response and may be delayed until the next scheduled scan to avoid unnecessary procedures.

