All subjects with brain metastasis must have MRI of the brain performed within 28 days prior to first dose of AMG 510. Subsequently, brain scans may be performed at any time if, in the judgement of the managing physician. All brain scans on protocol are required to be MRI unless MRI is contraindicated, and then CT with contrast is acceptable.

Radiological imaging assessment during the EOT visit should be performed only for subjects that discontinue treatment for a reason other than disease progression per **RECIST 1.1** guidelines.

Determination of disease response for clinical management of subjects will be assessed at the clinical sites per **RECIST 1.1**. Scans will be submitted to a central imaging core laboratory for archival, response assessment including **RECIST 1.1**, and/or exploratory analysis eg, volumetric and viable tumor measurements. Detailed information regarding submission of images to the central imaging core laboratory is found in the Site Imaging Manual.

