10.1.1.2.2 Secondary Endpoints

- DOR - defined as time from first evidence of confirmed PR or CR to disease progression or death due to any cause, whichever occurs first. Subjects without a duration ending event will be censored at their last evaluable disease assessment date. Progression will be based on an independent radiologic assessment of disease response per **RECIST** 1.1.
- DCR defined as CR + PR + stable disease rate measured as described for ORR.
- PFS - defined as time from first dose of AMG 510 until disease progression or death from any cause, whichever occurs first. Subjects who do not progress or die will be censored at their last evaluable disease assessment date. Progression will be on an independent radiologic assessment of disease response per **RECIST** 1.1.
- OS - defined as time from first dose of AMG 510 until death from any cause. Subjects who do not die will be censored at the date of last contact.
- PFS rate at 6 months and 12 months.
- OS rate at 12 months.
- Incidence and severity of adverse events.
- PK parameters of AMG 510 including, but not limited to, C_{max} , t_{max} , and AUC.
- **TTR - defined as time from first dose of AMG 510 until the first evidence of confirmed PR or CR.**

Approved

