2.1.3 Phase 2 (AMG 510 Monotherapy)

Objectives	Endpoints
Primary	

 To evaluate tumor objective response rate (ORR), assessed by RECIST 1.1 criteria, of AMG 510 as monotherapy in subjects with KRAS p.G12C mutant advanced solid tumors (NSCLC, colorectal cancer [CRC], and other tumor types). 	
 Objective response rate (ORR = complete response [CR] + partial response [PR]), assessed per RECIST 1.1. Response will be assessed by independent radiologic review. Complete response and PR require confirmatory CT or MRI repeat assessment 4 weeks after the first detection of response.
Secondary	

 To evaluate other measures of AMG 510 efficacy as monotherapy in subjects with KRAS p.G12C mutant advanced solid tumors by RECIST 1.1 (NSCLC, CRC, and other tumor types). 
 Duration of response (DOR) Disease control rate (DCR) Time to response (TTR) Progression-free survival (PFS) Overall survival (OS) PFS rate at 6 months and 12 months OS rate at 12 months 	
 Duration of response - defined as time from first evidence of confirmed PR or CR to disease progression or death due to any cause, whichever occurs first. Subjects without a duration ending event will be censored at their last evaluable disease assessment date. Progression will be based on an independent radiologic assessment of disease response per RECIST 1.1 Disease control rate defined as CR + PR + stable disease rate measured as described for ORR Time to response - defined as time from first dose of AMG 510 until the first evidence of confirmed PR or CR Progression-free survival - defined as time from first dose of AMG 510 until disease progression or death from any cause, whichever occurs first. Subjects who do not progress or die will be censored at their last evaluable disease assessment date. Progression will be on an independent radiologic assessment of disease response per RECIST 1.1. Overall survival - defined as time from first dose of AMG 510 until death from any cause. Subjects who do not die will be censored at the date of last contact. Progression-free survival rate at 6 months and 12 months Overall survival rate at 12 months

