No evaluable post-baseline tumor assessments, no death by data cutoff	Date of first dose	Censor
No surgical resection, no new anti-cancer therapy, did not withdraw consent to participate in the study and :		
Progression documented per RECIST v1.1 before any death by data cutoff	Date of first observation date of disease progression	Event
No progression, but death recorded by data cutoff	Date of death	Event
No progression nor death by data cutoff	Date of last evaluable assessment	Censor
Surgical resection/new anti –cancer therapy started or withdraw consent to participate in the study and:		
Progression documented per RECIST v1.1 before surgical resection/new anti-cancer therapy started or withdraw consent to participate in the study by data cutoff	Date of first observation date of disease progression	Event
Progression documented per RECIST v1.1 after surgical resection/new anti-cancer therapy started or withdraw consent to participate in the study and alive by data cutoff	Date of last evaluable scan before start of new ant-cancer therapy/surgical resection	Censor
Subject died subsequently on or prior to data cutoff	Date of death	Event
No progression nor death by data cutoff	Date of last evaluable scan before start of new anti-cancer therapy/surgical resection	Censor

Relative Dose Intensity:

Relative dose intensity is calculated as actual dose intensity / planned dose intensity, where

- Cumulative actual dose [mg] is defined as the total dose given during the study treatment exposure. For subjects who did not take any drug the cumulative actual dose by definition is 0 mg.
- Actual dose intensity for subjects with non-zero duration of exposure is defined as: cumulative actual dose [mg] / duration of exposure [days] where duration of exposure = date of last dose – date of first dose + 1. For subjects who did not take any drug the actual dose intensity is 0 mg/day.
- Cumulative planned dose is the per-protocol planned dose accumulated over the actual duration on study treatment.
- Planned dose intensity for subjects with non-zero duration of exposure is defined as: cumulative planned dose [mg] / duration of exposure [days] where duration of exposure = date of last dose – date of first dose + 1.

Safety Follow-Up:

It is defined as the subject visit up to 30 (+7) days after last dose of AMG 510 is received.

Study Day:

Post-study day: study day= (date – date of Study Day 1) + 1

Pre-study day: study day= (date – date of Study Day 1)

Study Day 1:

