9.1 General Considerations

Descriptive statistics will be provided for selected demographic, safety and efficacy data. Descriptive statistics on continuous data will include means, medians, standard deviations, minimums & maximums while categorical data will be summarized using frequency counts and percentages. For time-to-event variables, the Kaplan-Meier (KM) estimates and corresponding two-sided 95% confidence intervals for the median and quartiles will be provided. Graphical summaries of the data may also be presented. The K-M plot may also be provided.

Efficacy and safety analyses will pool together all tumor types and also present tumor types separately. Efficacy analysis for Phase 1 and Phase 2 will be analyzed separately. In addition, integrated safety analyses will be done by different planned dose levels and treatments (monotherapy or combination therapy) and phases, using the Safety Analysis Set.

Futility and efficacy thresholds in phase 1 and futility interim in phase 2 will be based on site-assessed disease response per RECIST 1.1. Primary, final, and any additional efficacy analyses will be based on an independent radiologic assessment of disease response per RECIST 1.1.

Nominal 95% confidence intervals will be calculated.

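### Site-called progression that the central reader does not confirm is censored in DOR and PFS, with no sensitivity analysis planned; the imaging stop rule does not say whose read counts

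*Supplement*

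**What the plan says.** **When imaging ends.** Protocol 7.5 states: "Radiologic imaging and tumor assessment will be performed until disease progression, start of new anticancer treatment, death, withdrawal of consent" or end of study. The imaging footnotes to Protocol Tables 2 and 6 follow the same line. None of them names the reader. The end-of-treatment scan is limited to patients who stop treatment for a reason other than progression.

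**Who reads.** Also in 7.5: "Determination of disease response for clinical management of subjects will be assessed at the clinical sites per" RECIST 1.1. Scans go to a central laboratory as well, but nothing provides for returning its read to the site before scanning stops.

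**Follow-up after treatment.** Protocol 7.2.5 and the matching footnotes say that "for subjects who discontinued study treatment without confirmed disease progression or start of subsequent anticancer treatment, tumor assessments will continue during LTFU" every 12 weeks. By contrast, "Subjects who had confirmed disease progression or started subsequent anticancer treatment" are followed by telephone. *Confirmed* is not defined for progression. Appendix D requires confirmation for CR and PR; for progression it mentions a repeat scan only when a new lesion is equivocal.

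**Endpoints.** For DOR, Protocol 10.1.1.2.2 and SAP 2.1.3 state: "Progression will be based on an independent radiologic assessment of disease response per RECIST 1.1". PFS is defined likewise, and death from any cause is an event for both. SAP 9.1 adds: "Primary, final, and any additional efficacy analyses will be based on an independent radiologic assessment of disease response per RECIST 1.1".

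**Censoring.** SAP Section 5, Table 1 (Main PFS Definition) censors a patient with neither progression nor death at "Date of last evaluable assessment". If new therapy has started, the date is the last evaluable scan before it. Death is an event, even after new therapy. DOR follows the same table. No row covers progression called by the site but not by the central reader.

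**Sensitivity analyses.** SAP Table 9 lists none for any endpoint, DOR and PFS included.

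**The concern.** One read appears to govern when scanning stops, and another defines the event. When the central reader calls progression no later than the site, nothing is lost. When the site calls it first, follow-up may end before the central reader has a scan on which to agree. If the patient is alive at cutoff, Table 1 treats the case like a patient in stable follow-up who has just not been scanned again. Kaplan-Meier assumes that censored patients carry the same future risk as those still observed. A patient whose site has just called progression probably carries more, so the curve would tend to sit too high.

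The stake is the durability evidence. Protocol 10.4.2 and SAP 7.2.2 set the cutoff so that durability of response can be shown, and the 6- and 12-month PFS rates are named secondary endpoints. The study is single-arm, so no control group shares the distortion. The SAP places the phase 2 primary analysis at 6 months of follow-up, when fewer of these patients will have died and so become events.

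**Working it through.** **Step 1. Trace a patient whose site has called progression through SAP Table 1.**

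| Central read | Status at cutoff | Table 1 result |
|---|---|---|
| Agrees | any | Event at scan date |
| Does not agree | Dead, with or without new therapy | Event at date of death |
| Does not agree | Alive, no new therapy | Censored at last evaluable scan |
| Does not agree | Alive, new therapy started | Censored at last scan before new therapy |

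Only the last two rows are a problem.

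**Step 2. Is there a figure in the plan to reproduce?** No. The plan gives no target median, rate or event count for DOR or PFS, and no discordance rate. Any size is therefore an illustration.

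**Step 3. Simulate PFS with deaths counted.** The scan schedule comes from Protocol 7.5: weeks 6, 12, 18 and 24, then every 12 weeks. Everything else is assumed:
- time to progression exponential, median 6 months;
- survival after progression exponential, median 4 or 8 months;
- follow-up uniform from 6 to 18 months;
- a fraction q of patients discordant, meaning that the central reader would see progression one scan after the site;
- 100,000 patients per scenario, with new therapy not modelled.

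The estimate is S(t) = product over event times up to t of (1 − d/n), where d is the number of events and n the number at risk. *As written*: concordant progression is an event at the site scan, death is an event at its date, and discordant patients alive at cutoff are censored at the site scan. *Continued*: imaging runs to central progression.

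6-month PFS:

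| q | Survival after progression | As written | Continued | Difference (points) |
|---|---|---|---|---|
| 10% | 4 months | 55.2% | 53.5% | 1.7 |
| 10% | 8 months | 55.6% | 53.4% | 2.2 |
| 20% | 4 months | 57.6% | 54.3% | 3.3 |
| 20% | 8 months | 58.9% | 54.4% | 4.5 |
| 30% | 4 months | 59.7% | 54.7% | 5.0 |
| 30% | 8 months | 61.9% | 55.1% | 6.8 |

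12-month PFS:

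| q | Survival after progression | As written | Continued | Difference (points) |
|---|---|---|---|---|
| 10% | 4 months | 28.4% | 27.9% | 0.5 |
| 10% | 8 months | 29.8% | 28.4% | 1.4 |
| 20% | 4 months | 29.8% | 28.4% | 1.4 |
| 20% | 8 months | 31.9% | 29.0% | 2.9 |
| 30% | 4 months | 30.7% | 28.8% | 1.9 |
| 30% | 8 months | 34.4% | 29.9% | 4.5 |

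With q = 0 the two rules coincide. For q from 10% to 30% the median is 8.28 months (the 36-week scan) under both rules.

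**Step 4. Robustness.** A rerun with a 28-week median time to progression and q from 10% to 30% gives differences of 1.6 to 6.5 points at 6 months and 0.7 to 4.6 at 12 months. The median stays at 36 weeks, except for about 38 weeks in the most extreme cell (30%, 8 months).

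**Step 5. How many patients are affected?** At q = 20%, 4.1% of all patients (4-month survival) or 7.1% (8-month) are discordant and censored alive. A further 7.7% or 5.5% are discordant but counted as events at death.

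**Step 6. What would a sensitivity analysis show?** Counting the site call as the event gives a 6-month PFS of 52.8% at q = 20% with 8-month survival. The continued-imaging value is 54.4% and the as-written value 58.9%. In this model the two analyses bracket the value that full imaging would give.

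**The case against.** The best defence has four parts.

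**The stop at site-read progression is an inference.** This stands in part. Section 7.5 names no reader, treatment may run to confirmed progression, and 7.2.5 keeps scanning patients who stop without it. If *confirmed* meant centrally confirmed, the gap would be narrower. The protocol does not say so, and 7.5 drops the word. Appendix D's request for further imaging covers symptomatic deterioration without objective progression, which is a different case. The Site Imaging Manual might settle the matter, but it is not among the documents.

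**Death is an event.** This stands, and it limits the effect. A reader might infer that everyone whose site calls progression is censored, or that only centrally read progression counts. Table 1 supports neither: patients whose progression the central reader confirms, and patients who die by cutoff, are events.

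**Any size is assumed.** This also stands. A simulation that ignores deaths could suggest a much larger rise at 12 months and a jump in the median. With deaths counted, the 12-month rise shrinks and the median barely moves. Only PFS was simulated. DOR shares the censoring rules, but its size was not calculated.

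**DOR and PFS are secondary and descriptive.** True: they carry no benchmark or decision rule. That lowers the weight of the point, but it does not explain why a known source of informative censoring has no planned check.

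**Conclusion.** The point holds as a gap in the plan and a risk of bias, not as a demonstrated bias. The plan has no rule for progression called by the site and not by the central reader, no sensitivity analysis for DOR or PFS, and two unreconciled statements of when imaging ends. Patients in this position who are alive at cutoff are informatively censored, and the likely direction is upward. Under the assumptions above, 10% to 30% discordance adds about 2 to 7 points to 6-month PFS and about 1 to 5 to 12-month PFS, with essentially no change in the median. With no discordance the effect is zero.

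A reader might go further and conclude that the reported durations will be overstated, or that the response result is compromised. The documents do not support the first without a discordance rate. They do not support the second either, because ORR does not pass through this censoring rule. This is a worthwhile, inexpensive improvement to the durability evidence.

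**What to change.** 1. **SAP Table 1 and Table 9.** Prespecify a sensitivity analysis of DOR and PFS in which progression called by the site without central progression is an event at the site's progression date. Keep the independent-read analysis as the main one.
2. **Discordance table.** Tabulate site against central progression by tumor type, with the number of discordant patients censored alive and the number counted as events at death.
3. **Wording.** Reconcile Protocol 7.5, 7.2.5 and the imaging footnotes to Tables 2 and 6, so that one statement says whose progression ends imaging and what *confirmed* means. Which rule to adopt is for the sponsor and investigators to decide.

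Items 1 and 2 need no new data, because site-assessed response is already used for the futility analyses (Protocol 10.4.1.3.2, SAP 9.1). The cost is a little extra programming and a supportive figure that may look less favourable. Item 3 is a text change.

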7.6 Patient-reported Outcomes

Patient-reported outcomes (PRO) questionnaires will be administered **via electronic tablet** to subjects enrolled into the phase 2 monotherapy part of the study.

The impact of treatment on disease-related symptoms and HRQOL will be evaluated in all subjects (regardless of tumor type) using the European Organization for Research and Treatment of Cancer Quality-of-life Questionnaire Core 30 (EORTC QLQ-C30). In addition, disease specific modules will be employed: QLQ LC13 and **NSCLC SAQ** for

NSCLC, and QLQ-Pan26 for Pancreatic Cancer. Treatment-related symptoms and impact on the subject will be assessed in all subjects (regardless of tumor types) using selected questions from the Patient-Reported Outcomes version of the Common Terminology Criteria for Adverse Events (PRO-CTCAE) library and a single item about symptom bother (GP5 of the FACT-G). Physical function will be assessed in all subjects regardless of tumor type using the EORTC QLQ-C30. Health-related quality of life will **also** be assessed in all subjects regardless of tumor type using the EuroQoL-5 Dimension (EQ-5D-5L).

The PRO questionnaires should be completed by the subject prior to any other clinical assessments and before receiving any study medications.

The EORTC QLQ-C30 is a 2-page, self-reporting 30-item generic instrument for use in cancer subjects across tumor types. It assesses 15 domains consisting of 5 functional domains (physical, role, emotional, cognitive, social), 9 symptom domains (fatigue, nausea and vomiting, pain, dyspnea, insomnia, appetite loss, constipation, diarrhea, financial difficulties), and a global health status or Quality of Life (QOL) scale ([Aronson et al, 1993](#)).

The supplementary disease specific module, QLQ-LC13, is a validated questionnaire to assess the impact of treatment on lung cancer-associated symptoms (cough, hemoptysis, dyspnoea and site-specific pain) and treatment-related side effects (sore mouth, dysphagia, peripheral neuropathy and alopecia) and pain medication. It contains 13 questions.

The NSCLC SAQ is a 7-item instrument intended to measure overall symptom severity (eg cough, pain, dyspnea, fatigue, and appetite) of NSCLC. The NSCLC SAQ is intended to assess clinically meaningful change in overall symptoms of NSCLC and is suggested by the FDA to be used in early phase studies so that information to support thresholds for clinically meaningful, within-patient change in the NSCLC-SAQ total score can be established in the context of use.

The QLQ-PAN26 is a questionnaire **consisting of 26 items** developed to assess the **symptoms and** impact of treatment on symptoms related to pancreatic cancer. This module will be utilized to assess the small but important disease and treatment related **HRQoL** changes in pancreatic cancer. For all items on the QLQ-PAN26, except satisfaction with health care, a higher score reflected worse **HRQoL**.

PRO-CTCAE is a subject-reported outcome measure developed to evaluate symptomatic toxicity in subjects on cancer clinical trials. The questionnaire was designed to be used as a companion to the CTCAE, the standard lexicon for adverse event reporting in cancer trials. PRO-CTCAE item library version 1.0 is comprised of 124 individual questions developed to elicit 78 symptomatic AEs from subjects using between one to three attribute questions (ie, frequency, severity, and/or interference of the AE), (Basch et al, 2014). The recall period for PRO-CTCAE is the past 7 days. The PRO-CTCAE has been tested and validated in terms of construct validity, test-retest reliability, and item responsiveness (Dueck et al, 2015). In this study, the PRO-CTCAE will be administered via electronic tablet.

The specific questions which will be administered to subjects in this study will be selected from the PRO-CTCAE item library following a review of the data from the phase 1 dose exploration part of AMG 510 in *KRAS p.G12C* subjects and consideration of potential toxicities which may be relevant to future comparisons of AMG 510 to current standards of care. A customized form to collect these data will be developed using the online tool available at <https://healthcaredelivery.cancer.gov/pro-ctcae/builder.html>.

The GP5 of the FACT-G is a single item “I am bothered by side effects of treatment” rated on a 5-point Likert scale from “not at all” to “very much” is an item included in the Physical Well-Being subscale of the PRO assessment instrument Functional Assessment of Cancer Therapy Tool General form (FACT-G). It has been evaluated and validated as a useful summary index of side effect impact or burden to the individual subject (Pearman et al, 2018).

The EQ-5D-5L questionnaire is a 2-page, standardized instrument for use as a measure of health outcome developed by the EuroQol group (Rabin and de Charro, 2001). It is comprised of a 5-dimension health status measure and a visual analogue scale. The 5-dimension health status measure evaluates: mobility, self-care, usual activities, pain/discomfort, and anxiety/depression based on a 5-level scale: no problems, slight problems, moderate problems, severe problems, an extreme problem. The visual analogue scale records the subject's self-rated health on a vertical, visual analogue scale where the endpoints are labelled 'Best imaginable health state' and 'Worst imaginable health state'. The EQ-5D-5L takes about 3 minutes to complete.

